C.4.1 Study Design. This is a pragmatic, cluster randomized comparative effectiveness trial. Given the complexity of systems and processes needed to implement SMAs, and the possibility of contamination effects, randomization will be clustered at the practice level using covariate constrained randomization.⁵⁵⁻⁵⁷ Twenty-two practices will be randomly assigned to either standardized or patient-driven diabetes SMAs (10 per condition). During the 24-month implementation period, each practice will conduct SMAs with around 8 cohorts of 8 to 10 patients each (ultimately yielding up to 72 patients per practice). The initial plan is that cohorts of adult patients with T2DM will progress through 6 weekly SMA sessions, and a new cohort will begin every 3 months, but practices can choose their own timeline. A mixed-methods evaluation will include quantitative (practice and patient-level surveys, electronic health records (EHR), and participation and intervention fidelity tracking data) and qualitative (practice and patient interviews, observation) components.

Sample Size and Power Calculations: Previous power calculations used 1,440 total patients, which is not feasible given recruitment challenges by practices. We are expecting N (total) = 22 clinics, 1,000 patients (11 clinics and 500 patients

PRINCIPAL INVESTIGATOR (LAST, FIRST, MIDDLE): [name]

per condition), allowing for ~15-20% attrition (leaving 400 patients per arm). However, we are estimating power based on 20 practices and provide a possible range of potential power to detect main effects. We estimated the minimum effect sizes detectable for different power calculations for various numbers of practices and patient sample sizes and intraclass correlations (ICC; see table below), with effect sizes of approximately .29 to .35 for intent-to-treat analyses of primary outcomes with a type-1 error rate of .05. Power for planned subgroup analyses for patient characteristics (e.g., mental illness, health literacy) is also shown. An effective sample size of 67 per group is required to detect a medium linear trend effect between groups (increasing from 0 to .5SD) using general linear mixed models with random slopes and intercepts.⁵⁸

| Practices per arm: N | Patients per practice: N | With 15-20% attrition: N | ICC | Effective sample size | Detectable difference (effect size) | Power |

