Patient-level clinical outcomes (Aim 2a). We will gather clinical outcomes data (HbA1c, blood pressure, body mass index) from participating practices’ EHRs. All encounter data (dates, locations, visit and provider types, diagnosis codes), lab results and vital signs measures from 9 months before through 9 months after each patient’s initial SMA visit will be requested. Diagnosis codes (ICD-9/10) will be used to compute a comorbidity index⁷⁷ and to corroborate diagnosis of mental illness. Prescription data will be used to assess insulin dependence.

Patient reach and engagement in SMAs (Aim 2b). We will assess reach and engagement in terms of acceptance (i.e., what proportion of patients agree to participate in SMAs?) and participation (i.e., what proportion of SMAs do patients attend?), defined by Raue and Sirey.⁷⁸ Attendance at each session and total attendance for each of the 6 sessions, as well as any reasons for dropout, will be recorded by the SMA coordinators in a spreadsheet.

Practice-level outcomes measures (Aim 2c).

Practice quality of care, team-based care, and resource requirements. We will administer several validated practice-level measures to all practice staff and providers, as summarized in Table 5. Practice staff and providers in participating practices will be asked to complete survey measures assessing aspects of practice context (which often influence efforts to improve diabetes care⁷⁹), including measures of relational coordination (using the Relational Coordination Survey,⁸⁰ a measure of team-based care and important factor in chronic illness care in primary care teams⁸¹), practice CCM-consistent care (using the Assessment of Chronic Illness Care [ACIC])⁸², and role in SMAs. Those involved in SMAs will also complete measures of SMA resource requirements using a time-driven activity-based costing [TDABC] framework⁸³ to assess staff time use, workflows, required materials and supplies, and other resources needed to deliver each SMA model, distinguishing between early and late implementation phases. To assess practice culture, the Practice Culture Assessment will be administered to all practice staff.

Table 4. Outcomes, Measures and Data Sources

| Outcome Domain | Construct | Source | Metric/Measure | Timing | Respondent / Unit | Administered /Collected by |
|--|---------------------------------|-----------------------------------|--|--|-------------------------|--|

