Clinical outcomes data for each participating patient will be extracted from the participating practices' EHR for the period 9 months before and after each patient's involvement in SMAs using chart review and extracts from practice backend EHR databases. EHR extracts will be requested for all patients enrolled to date at the mid-point and end of the implementation phase. Patients with diabetes are typically seen in primary care every 3 months, or more often if poorly controlled, and data on HbA1c, body mass index (BMI), and blood pressure are collected routinely at these visits. Using data collected in the course of routine care is a pragmatic feature of this project, reducing costs and burden to practices and patients. Because all data will be gathered from the practice EHRs, availability of data will not be dependent on participation in interventions, allowing robust estimates of effectiveness of interventions among those for whom they are intended as well as sub-analyses among those who participate. These EHR extracts will include patient survey data, as described above. The SMA coordinator will provide a list of patients to a practice data analyst (an existing role in participating practices). The analyst will extract the requested data into flat files following specifications provided by the research team, strip direct identifiers to create a HIPAA limited data set, and create a random unique patient identifier. Data will be transferred to the research team using a secure cloud-based encrypted transfer mechanism (Egnyte.com), cleaned, and standardized across practices according to the OMOP common data model using middleware developed by [name] and other local informatics colleagues.⁸⁴ Extract specifications will be refined in collaboration with analysts following the initial extract and review of data quality following recommendations for data quality checking in CER (e.g., assessing attribute domain constraints including ranges, relational integrity rules, historical data rules including temporal components, and missingness).⁸⁵ HIPAA data use agreements will be executed with participating practices prior to transfer of data. Drs. [name], [name] and [name] routinely use this approach through our data network infrastructure.

Practice surveys will be administered at baseline (pre-implementation state), 6-9 months (early impressions) and within 2 months of completion of SMAs (final impressions) in the implementation phase; practices will be given the

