In the model above we use practice level random effects. However, it is possible that groups (within practices) are a greater source of variation than practices per se. Therefore, we will estimate variance components for groups within practices and retain both random effects if there is sufficient variability. If it is not possible to retain both group and practice random effects, we will test each separately and examine model fit and variance components to determine which to retain.

To test hypothesis II (comparing clinical outcomes): Outcomes for these analyses will be obtained from EHR data covering 9 months' post-baseline for each patient. The baseline measure for each clinical outcome will be defined as the last recorded value prior to enrollment in the study. All subsequent clinical measures through 9 months after enrollment will be used in analysis. Analytic approaches will be similar to those described for hypothesis 1, with time will be coded

PRINCIPAL INVESTIGATOR (LAST, FIRST, MIDDLE): [name]

as time since baseline. Random coefficient growth curve models will be used to determine whether trajectories for patients in standard SMA practices differ from patients in patient-driven SMA practices (time x arm interaction term in mixed model notation).

Hypothesis III. Compared to standardized diabetes SMAs, practices using patient-driven diabetes SMAs will exhibit greater improvements in quality and team-based care, as measured by the Relational Coordination Survey and the Assessment of Chronic Illness Care.

To test ***hypothesis III (comparing patient reach and engagement)***. The outcomes for these analyses will be 1) acceptance of services (Y/N), and 2) number of SMA sessions attended. General or generalized linear mixed effects models (depending on distribution of outcomes variable) with a practice random effect will be used for analysis. In addition to including covariates as described above, we will test whether mental illness is a moderator of intervention effectiveness. This will involve including a main effect for mental illness, along with an arm x mental illness interaction term (mixed model notation).

To test ***hypothesis IV (comparing practice quality and team based care)***: Outcomes for this analysis will be scores on the relational coordination survey and the ACIC at baseline, 9, and 24 months. Analytic approaches will be similar to those described for hypotheses I and II.

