| Estimated number of potentially eligible study participants (describe how this number was determined [e.g., EHR, claims data, clinic logs, administrative data, other]): | Participating practices see on average ~500 unique adult patients/year with diabetes (estimated from EHR data) |
| Total number of study participants expected to be screened: | N/A (screening does not apply) |
| Total number of study participants expected to be eligible of those screened: | N/A |
| Target sample size (use same number stated in milestones): | 1000 patients (45.5/practice *22 practices) |
| If applicable, total number of practices/centers that will enroll participants: | 22 |
| Projected month first participant enrolled (month after project initiation): | Month 9 (pilot cohort) |
| Projected month last participant enrolled (month after project initiation): | Month 45 |
| Projected rate of enrollment (anticipated number enrolled per month of enrollment period): | 1 new cohort of 8-10 patients per practice every 3 months |
| Estimated percentage of participant dropout: | 15-20% |

E. Investigators and Environment (Criterion 4)

As noted above, this study will take place in the CU-SOM's ACCORDS in collaboration with member practices of the SNOCAP PBRNs. The research team has considerable expertise and experience in practice-based research, diabetes self-management interventions, study design and analysis, implementation science, stakeholder engagement, mental and behavioral health, and mixed methods research. [name], the PI, is a social health psychologist and health services researcher with experience in mixed methods research and application of psychological theory to the design and testing of interventions for chronic disease management in primary care settings. She is the Associate Director of SAFTINet, a distributed data network and SNOCAP-affiliated PBRN with infrastructure linking clinical, claims and patient-reported data. With the support of the Co-PI and Co-investigators, with whom she has a track record of successful collaboration, she is well-prepared to lead this study. [name], the Co-PI, is a clinical psychologist and director of research and evaluation at the Jefferson Center for Mental Health with a history of successful collaboration with the clinics engaged in this study. She has extensive experience in stakeholder engagement, mental health and primary care, and leading implementation of similar chronic disease management programs.

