2. CONDUCTING THE STUDY: Stakeholder partners (patients and practice representatives) will participate in the study conduct by reviewing enrollment numbers and data collection, and suggesting changes in approach should the rate of enrollment lag behind milestone goals - each providing their own perspective. There are often unforeseen barriers and challenges in implementation; stakeholders can also contribute to troubleshooting these barriers. The stakeholders may have to decide, for instance, the extent to which elements determine to be required elements need to be adapted or modified. Health plan stakeholders will inform reimbursement plans. Quarterly stakeholder conference calls are planned throughout the 24-month implementation phase.

3. DISSEMINATING THE STUDY RESULTS: Patient partners will be engaged in dissemination by 1) contributing to interpretation of results from the patient and family perspective, 2) translating findings into messages that help other patients make decisions about whether or not to participate in SMAs, 3) participating in conference presentations (co-authoring and attending conferences), 4) contributing to framing and conclusions in published manuscripts (as co-authors). Additionally, depending on the results, patient partners may advise adding or eliminating other features of SMAs, and may serve as advocates to the practices and payers to support maintaining the patient-driven SMA model. Similarly, practice and health plan stakeholder representatives will contribute to interpretation of findings from the practice and health system perspectives, and to dissemination in the peer-reviewed literature. They will help prepare briefs on the value of patient-driven versus standardized SMAs and other information relevant to potential adopting organizations such as personnel, space and scheduling requirements, reimbursement strategies, and related issues. Practice and health plan stakeholders will also ultimately determine whether to promote adoption of standardized or patient-driven SMAs, and to advise the research team on opportunities for further research on additional variations of SMAs and/or larger scale implementation and dissemination trials.

DISSEMINATION AND IMPLEMENTATION POTENTIAL

For detailed instructions, refer to the Application Guidelines for your PFA. Do not exceed two pages.

A. Describe the potential for disseminating and implementing the results of this research in other settings.

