This study involves both primary data collection via qualitative and self-report surveys and a secondary analysis of existing clinical, demographic and administrative data from local practice electronic health records ("EHR data") maintained by participating practices. Intervention implementation strategies informed and refined through focus groups and qualitative interviews will be developed and pilot-tested during the first year, implemented in years two and three, and assessed in year four. A cluster randomized, pragmatic comparative effective trial will be utilized, where practices will be assigned either to standardized or patient-driven SMA intervention groups to compare the effectiveness of the intervention strategies. Patients in standardized groups will receive the standard intervention model at the participating sites. Patients in patient-driven groups will receive enhanced SMAs as developed during year one.

1. Practice Interviews: Selected practice staff and providers in participating practices will be asked to participate in key informant interviews to assess practice culture and context. These interviews will be completed at baseline and again at 9 and 24 months.
2. Practice Surveys: All practice staff and providers in participating practices will be asked to complete survey measures assessing team-based care and quality of care. These surveys will be completed at baseline and again at 9 and 24 months.
3. Patient Interviews and out-of-pocket cost surveys: Patient interviews and out of pocket cost and time surveys will assess patient experience as well as patient-incurred costs of SMAs specifically and diabetes care more generally. Interviews will be conducted 35-40 purposefully selected patients sampled from each of the experimental conditions.
4. Patient Reported Outcomes Measures: Patient surveys assessing outcome measures selected by stakeholders or consistent with the conceptual model will be completed at the first SMA session and the last SMA session, as part of clinical care. These data will be linked with clinical outcome data and stored in local data bases.

PRINCIPAL INVESTIGATOR (LAST, FIRST, MIDDLE): [name]

5. Patient-level Clinical Outcomes data from the EHR:

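### The final EHR extract falls at the end of implementation, so any cohort starting less than 9 months before it will have truncated clinical follow-up for Hypothesis II

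*Combined protocol and SAP*

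**What the plan says.** Under quantitative data collection in C.4.4.2c, the protocol says of clinical outcomes: "EHR extracts will be requested for all patients enrolled to date at the mid-point and end of the implementation phase". It names chart review as a second route but gives it no date.

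The 9-month window is stated three times, each with a different starting point:

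- **Patient-level clinical outcomes (Aim 2a), C.4.4.2c:** the request covers "lab results and vital signs measures from 9 months before through 9 months after each" patient's initial SMA visit.
- **Quantitative data collection, C.4.4.2c:** the window is 9 months before and after the patient's involvement in SMAs.
- **Hypothesis II, C4.4.2d.1:** "All subsequent clinical measures through 9 months after enrollment will be used in analysis". The same paragraph asks for data over 9 months post-baseline for each patient.

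The calendar comes from four places:

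- **C.4.1:** "During the 24-month implementation period, each practice will conduct SMAs with around 8 cohorts of 8 to 10 patients each". The initial plan is six weekly sessions, and "a new cohort will begin every 3 months", although practices may set their own schedule.
- **Conducting the Study (engagement plan):** "Quarterly stakeholder conference calls are planned throughout the 24-month implementation phase".
- **Table 5:** first enrolment at Month 9, last at Month 45, target 1000 patients at 45.5 per practice.
- **Human Subjects Involvement, Characteristics and Design:** strategies are "implemented in years two and three, and assessed in year four".

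**The concern.** The data-collection rule and the analysis rule cannot both hold for a cohort that starts late. If the last pull happens when implementation ends, a cohort starting in the preceding 9 months has not yet accrued the follow-up that Hypothesis II specifies.

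The text does not suggest that the implementation phase includes a follow-up tail. The final practice survey is due within 2 months of the SMAs finishing, and Table 4 puts that survey at 24 months. The phase therefore appears to end at about the time the groups end.

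At stake is the later part of the HbA1c, blood pressure and BMI trajectories. Clinical values are expected roughly quarterly. A patient cut off at 3 months may contribute one post-baseline value where about three were intended, and one cut off at 6 months about two. The 6-to-9-month part of the growth curve would then rest mainly on earlier cohorts, and a report of 9-month follow-up would not be accurate for everyone.

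**Working it through.** **Inputs.** Cohort spacing of 3 months, six weekly sessions, 8 to 10 patients per cohort and a 24-month period (C.4.1); 45.5 patients per practice and enrolment over Months 9 to 45 (Table 5); a 9-month window (Hypothesis II).

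**1. Reproduce the plan's figures.** 24 / 3 = 8 cohorts. 8 × 9 patients (midpoint of 8 to 10) = 72 per practice, as C.4.1 states. 72 × 20 practices = 1440, the target that C.4.1 now calls infeasible.

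**2. Eight cohorts, extract at month 24.** Available follow-up = 24 − start month.

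| Start month | 0 | 3 | 6 | 9 | 12 | 15 | 18 | 21 |
|---|---|---|---|---|---|---|---|---|
| Months to extract | 24 | 21 | 18 | 15 | 12 | 9 | 6 | 3 |

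Cohorts 7 and 8 fall short: 2/8 = 25%. Six weekly sessions span 5 weeks (about 1.15 months). Counted from the last session, 3 of 8 fall short, with about 7.9, 4.9 and 1.9 months.

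**3. Current target, extract at month 24.** 45.5/10 = 4.55 and 45.5/8 = 5.69, so five or six cohorts.

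- Five cohorts start at months 0 to 12; the last completes 9 months at 12 + 9 = 21.
- Six cohorts start at months 0 to 15; the last completes at 15 + 9 = 24.

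Counted from first session, none is truncated. Counted from the last session, the sixth cohort needs 15 + 1.15 + 9 = 25.15 months, about 5 weeks past the extract. With six cohorts there is no slack: if the first starts at month 3, the sixth starts at month 18 and has 6 months.

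**4. Table 5 calendar.** Assume even enrolment over 45 − 9 = 36 months.

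- Extract at Month 45: patients enrolled after Month 36 fall short, 9/36 = 25%, and the last has no follow-up.
- Extract at Month 48 (an assumption; the plan does not schedule one then): (45 − 39)/36 = 16.7%, and the last has 3 months.

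**5. Extract date needed for full follow-up from first session.** With eight cohorts, 21 + 9 = month 30. On the Table 5 calendar, 45 + 9 = Month 54.

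**6. Upper illustration of the cost.** Effective n = km/(1 + (m − 1)ICC); detectable d = (1.960 + 0.842) × √(2/effective n). For the first row of the power table (k = 10, m = 44.5, ICC 0.03), 445/2.305 = 193 and d = 0.285, matching the stated 193 and .29. If 25% of patients were discarded outright, m = 33.4, effective n = 169, d = 0.304, and power at .29 is 76%. The planned model discards no one for short follow-up, so the real loss from truncation is smaller.

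**The case against.** The strongest reply is that the problem may be small or absent on the schedule now intended. The eight-cohort pattern belongs to the 1440-patient plan. At 45.5 patients per practice, prompt starts at 3-month spacing leave everyone with 9 months from first session. Practices may also set their own timeline. This stands, and it rules out a single headline percentage. It does not remove the conflict: nothing requires cohorts to start early enough, and last enrolment at Month 45 points to slower recruitment.

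A second reply is that chart review is undated and an assessment year follows implementation, so a later pull may be intended. That is possible, but none is assigned.

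A third reply is that the growth model uses all available values, so late cohorts are shortened and not lost. This also stands.

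A reader might be tempted to infer more than the documents support:

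- **That a quarter of patients will be truncated, or that late cohorts can never reach 9 months.** Both depend on the calendar, as the working shows.
- **That follow-up overruns the project because Month 54 is later than Month 48.** No project end date is stated, and the human-subjects section that gives the year-four assessment still carries the 1440 target. The date mismatch is real, but it does not demonstrate an overrun.
- **That the arm comparison is biased.** The cut-off is administrative and the same rule applies in both arms; no differential effect is shown.
- **That late cohorts differ systematically in delivery mode or practice experience.** The note on mode of delivery in C.4.3.1c says that return to in-person visits varied by practice. It does not state the mode of late cohorts.

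**Conclusion.** The concern holds as a conflict between the extract schedule and the Hypothesis II window, and it should be fixed. Any cohort starting less than 9 months before the final extract has incomplete HbA1c, blood pressure and BMI follow-up.

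The share is 25% on the eight-cohort schedule. It is zero from first session for five or six cohorts starting at month 0, with a sixth cohort about 5 weeks short if the window runs from the last session. It is about 25% with even enrolment over Months 9 to 45 and a Month 45 extract. These figures assume regular spacing or even accrual, which the plan does not require.

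The consequence is reduced precision in the late part of the trajectory. DDS-17 is measured at the first and last session and does not depend on this window.

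Separately, a 36-month enrolment span ending at Month 45 does not fit a 24-month implementation in years two and three.

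**What to change.** 1. Schedule the final EHR extract, or one top-up pull, at least 9 months after the last enrolled patient's anchor date, plus normal EHR lag.
2. Choose one anchor (initial SMA visit, end of involvement, or enrolment) and use it in both C.4.4.2c statements and in the Hypothesis II analysis.
3. Reconcile the dates in C.4.1, Table 5, the Conducting the Study section and the human-subjects section, and say when the implementation phase ends on the Table 5 calendar.
4. If the project end prevents a later pull, report the percentage of patients with full follow-up and describe the window as up to 9 months.

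The cost is one later data pull by the existing practice analysts, and Hypothesis II results that arrive some months later.
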